#### **VIII. POTENTIAL BENEFITS**

This research may help physicians and scientists explore the potential contribution of vascular maladaptations to SCI related bone loss, with major implications in treating osteoporosis. Subjects will not directly benefit from participation in this protocol.

#### **MONITORING AND QUALITY ASSURANCE**

The research coordinator will be responsible for monitoring the completeness of all data and source documents. The Principal Investigator will monitor the informed consent procedures in accordance with the Informed Consent Compliance Checklist of Partners HealthCare Systems HRQIP. The subjects data/protocol adherence will be monitored by the research coordinator at each step in the study including. Checklists and note pages are used to note any deviations or omissions from the protocols. The Cardiovascular Research Laboratory Medical Emergency

## PARTNERS HUMAN RESEARCH COMMITTEE

### DETAILED PROTOCOL

Safety Plan will be followed in the case of an adverse medical event. Any clinical/health related issues would be immediately presented to the subject (i.e. abnormal EKG, blood chemistries, etc) to determine appropriate notification (ie. current physician or appropriate specialist) .Based on the seriousness of the situation a physician may be contacted to provide clinical guidance on the appropriate course of action. Event assessment and follow-up will be done by the PI as needed on a case by case basis.

This study will be conducted in compliance with the protocol, International Council for Harmonization/Good Clinical Practice requirements(ICH/GCP) and applicable state, local and federal regulatory requirements.

#### **Reporting to Partners IRB:**

Reports of *unanticipated problems involving risks to subjects or others* are to be submitted through Insight/eIRB within 5 working days/7 calendar days of the date the investigator first becomes aware of the problem.

#### **Reporting Unanticipated Problems that are Adverse Events**

Any unanticipated untoward or unfavorable medical occurrence, including abnormal sign (for example, abnormal physical exam or laboratory finding), symptom, or disease, that indicates that the research places subjects at increased risk of physical or psychological harm than previously known or recognized are to be submitted through Insight/eIRB as an Other Event, Adverse Event. The investigator must provide the following information in the report:

- (1) a detailed description of the adverse event;
- (2) the basis for determining that the event is unexpected in nature, severity, or frequency;
- (3) the basis for determining that the event is related or possibly related to the research procedures;
- (4) the basis for determining that the research places subjects at an increased risk of harm (i.e., a serious adverse event); and
- (5) whether any changes to the research or other corrective actions are warranted.

NOTE: The PHRC does not accept sponsor IND/IDE safety reports describing adverse events that have occurred at sites other than those subject to this policy unless the report is of an incident that is:

- (1) serious; (2) unexpected or unanticipated; (3) related to the investigational drug/device; and
- (4) suggests that subjects are at an increased risk of harm and as such warrants changes in the research, consent process, or informing subjects. IND/IDE safety reports that warrant changes are to be submitted through Insight/eIRB as an Amendment.

#### **Reporting Unanticipated Problems that are not Adverse Events**

All other unanticipated incidents, experiences, information, outcomes, or other problems that indicate that the research places subjects at an increased risk of physical, psychological, economic, legal, or social harm than was previously known or recognized are to be submitted through Insight/eIRB as an

Other Event. The investigator must provide the following information in the report:

- (1) a detailed description of the unanticipated problem;
- (2) the basis for determining that the problem is unexpected;
- (3) the basis for determining that the problem indicates that the research places subjects at an increased risk of harm; and
- (4) whether any changes to the research or other corrective action are warranted.

## PARTNERS HUMAN RESEARCH COMMITTEE

### DETAILED PROTOCOL

#### **Reporting to the National Institute of Arthritis and Musculoskeletal and Skin Disease (NIAMS) and Safety Officer ([name]).**

This protocol has funding from NIAMS. NIAMS has appointed a Safety Officer, [name], to act in an advisory capacity to the NIAMS to monitor participant safety, evaluate the progress of the study, to review procedures for maintaining the confidentiality of data, the quality of data collection, management and analyses.

The Principal Investigator (PI) will report unanticipated problems (UPs), serious adverse events (SAEs) and protocol violations that impact participant safety to the NIAMS and the Safety Officer, (through the Executive Secretary, KAI-Research) within 48 hours of the PI becoming aware of the event. KAI facilitates the review of the expedited reporting of these events by the Safety Officer. The Safety Officer will review the Safety Reports submitted by the PI to KAI twice a year. KAI facilitates the review of these reports by the Safety Officer and the NIAMS, and provides the final review comments to the PI when the review is complete. During the course of the study, ad hoc meetings may be called by the NIAMS or Safety Officer at any time to discuss potential safety issues.

#### Definitions:

Adverse event means any untoward or unfavorable medical occurrence in a human subject, including any abnormal sign (for example, abnormal physical exam or laboratory finding), symptom, or disease, temporally associated with the subject's participation in the research, whether or not considered related to the subject's participation in the research (modified from the definition of adverse events in the 1996. International Conference on Harmonization E-6 Guidelines for Good Clinical Practice).

Serious adverse event means any event temporally associated with the subject's participation in research that meets any of the following criteria:

- results in death;
- is life threatening (places the subject at immediate risk of death from the event as it occurred);
- requires inpatient hospitalization or prolongation of existing hospitalization;
- results in a persistent or significant disability/incapacity;
- results in a congenital anomaly/birth defect; or
- any other adverse event that, based upon appropriate medical judgment, may jeopardize the subject's health and may require medical or surgical intervention to prevent one of the outcomes listed above (examples of such events include allergic bronchospasm requiring intensive treatment in the emergency room or at home, blood dyscrasias or convulsions that do not result in inpatient hospitalization, or the development of drug dependency or drug abuse).

# PARTNERS HUMAN RESEARCH COMMITTEE

## DETAILED PROTOCOL

*Possibly related to the research* means there is a *reasonable possibility* that the adverse event, incident, experience or outcome may have been caused by the procedures involved in the research (modified from the definition of *associated with use of the drug* in FDA regulations at 21 CFR 312.32(a)). *Reasonable possibility* means that the event is more likely than not related to participation in the research or, in other words, there is a >50% likelihood that the event is related to the research procedures.

# PARTNERS HUMAN RESEARCH COMMITTEE

## DETAILED PROTOCOL

### I. BACKGROUND AND SIGNIFICANCE

All tissues of the human body require adequate perfusion to provide oxygen and nutrients to meet metabolic demands. It has been long recognized that the arterial system in bone is of overwhelming importance, adequate circulation being necessary for nearly all skeletal functions, including development, growth, homeostasis, and repair. [1], [2] There is an extensive network of arteries, arterioles, and capillaries that supplies blood flow to bone and without adequate circulation bone cannot maintain its integrity. [3] For example, inadequate flow has been associated with bone loss,[4] impaired growth,[5] and delayed fracture healing.[6]

Despite the appreciation of the importance of blood circulation to bone health, the regulation of blood flow to bone has been relatively unstudied in humans and the mechanisms that regulate bone blood flow are not well understood. The majority of work in bone perfusion has been in various animal models (mice, rats, rabbits, dogs, cats, etc.) with the preponderance of data suggesting that there are key systemic effectors of acute changes in bone perfusion. One of the potential factors controlling blood flow regulation is the sympathetic nervous system, the bone vasculature being innervated by a rich network of sympathetic nerves. Although no studies in humans have been conducted, most of animal data demonstrates that sympathetic activation reduces blood flow to bone. Application of norepinephrine decreases blood flow to both intact bone [7], [8] and isolated bone. [9] Likewise, stimulation of sympathetic nerves decreases flow to bone [7] via alpha-adrenergic receptor activation.[9] Moreover, the smooth muscle of the arterioles in bone respond as expected to infused vasodilators and vasoconstrictors.[10], [11] Hence, the sympathetic innervation of bone vasculature serves a functional purpose in the control of blood flow. If this were not the case, independent of the link between bone metabolism and bone flow, the arterial network in bone would act as a simple pressure passive system. Here, we propose to investigate the role of vascular sympathetic activity in blood flow regulation in humans.

A critical limitation to the study of bone blood flow in humans has been the lack of noninvasive assessments. The dense nature of bone makes it difficult to investigate perfusion and the techniques used to quantify circulation in other tissues are either difficult or impossible to apply to bone *in vivo*. We recently developed a custom-made near infrared spectroscopy (NIRS) device that can non-invasively assess blood content in bone. [12] While NIRS has been used to assess perfusion in soft tissue,[13], [14] it has not been extensively used to assess perfusion in bone. However, NIRS has been shown to provide reproducible results in controlled conditions,[15] and can track dynamic changes in bone perfusion.[16], [17] In our preliminary work, we used NIRS to assess physiological changes in blood content in the tibial cortical bone in humans. Although our preliminary work is intriguing, it provided insufficient insight to regulation because this study was unable to disentangle the various possible contributors to bone perfusion. Thus, we aim to extend our preliminary work by examining the response of tibial perfusion to vascular sympathetic activity and systemic perfusion pressure in healthy individuals via NIRS monitoring. In addition, we will contrast these responses with those seen in individuals with spinal cord injury (SCI). SCI represents a human 'model' of chronic reduced loading with loss of sympathetic regulation below the level of injury that alters control of bone perfusion. Contrasting the response of tibial perfusion to vascular sympathetic activity and systemic perfusion pressure in able-bodied individuals and individuals with SCI will set the basis for future work that will define whether alterations in perfusion may relate to pathophysiologies of bone.

### Hypothesis

# PARTNERS HUMAN RESEARCH COMMITTEE DETAILED PROTOCOL

We hypothesize that bone blood perfusion decreases proportional to increases in leg vascular sympathetic outflow.

## II. SPECIFIC AIMS

- 1) Determine the effect of increased vascular sympathetic activity with maintained blood pressure on tibial perfusion.
- 2) Determine the effect of increased vascular sympathetic activity with increased systemic pressure on tibial perfusion.
- 3) Compare the changes in tibial perfusion in response to systemic factors between able-bodied and those with SCI.

Knowledge of tibial perfusion in response to increased sympathetic outflow, with or without changes in systemic pressure, will allow us to determine the sympathetic contribution to bone blood flow.

## III. SUBJECT SELECTION

### **Inclusion criteria**

It is anticipated that 34 healthy males and 34 healthy females aged 18 to 40 years will be recruited and enrolled for this study.

Also, we anticipate we will recruit 17 males with SCI, aged 18 to 40 years, with injuries American Spinal Injury Association Impairment Scale (AIS) A and B and C, with full hand function. We will only enroll males with SCI since the SCI population is predominantly male (about 75%).

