### **Exclusion criteria (for both able-bodied and SCI groups)**

Clinical signs or symptoms of heart disease, hypertension, coronary disease, diabetes, other neurological disease, cancer, recent weight change >15 pounds, abnormal resting ECG, pregnant and/or breastfeeding women, underweight and obese individuals (body mass index between 18.5 and 29.9), use of amphetamines (Ritalin, Adderall, Concerta) in the past 48 hours, tibial fracture or tibial stress fracture in the past year.

In addition, those with SCI will have no extreme spasticity to avoid spontaneous contractions and cannot be on baclofen due to its potential autonomic effects.

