#### **Detailed procedures**

Throughout the protocol, able-bodied volunteers will be fully instrumented for measurements of tibial blood flow, muscle/bone sympathetic activity, popliteal blood flow velocity, ECG, beat-by-beat arterial pressure, brachial arterial pressure, and respiration (see Measurements below). All those with SCI enrolled in this study will have complete injuries and thus vascular sympathetic control is disrupted below the level of injury. Hence, in individuals with SCI the arterial network in bone might act as a simple pressure passive system. Given the disrupted vascular sympathetic control, in those with SCI we will not record muscle/bone sympathetic activity.

In able-bodied, we will use direct microneurographic measures of nervous activity to the lower leg vasculature in the common peroneal nerve as a measure of sympathetic activity to the bone

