## PARTNERS HUMAN RESEARCH COMMITTEE DETAILED PROTOCOL

Cold pressor test and sustained isometric handgrip will be used to increase sympathetic nervous activity, with increased systemic pressure.

The cold pressor test provokes a nociceptive response that causes increases in sympathetic activity, blood pressure, and heart rate [23]. Past work showed that these responses are water temperature dependent. Graded increases in sympathetic activity, accompanied by parallel increase in arterial pressure, were seen during immersion at 0 and 7°C, but not at 14°C [24].

A 5 minutes resting baseline will be obtained prior to the subject performing the cold pressor test. Afterwards, participants will undergo a cold pressor task, consisting of immersion of a hand for 3 min in 0°C water. This will be followed by 3 minutes of recovery data collection.

Isometric handgrip to fatigue (IHE) results in time-dependent, progressive increases in peroneal nerve sympathetic outflow and blood pressure [25]. With sustained handgrip forces greater than 25% of maximal voluntary contraction, sympathetic activity increases progressively to end exercise. Hence, IHE provides a strong stimulus for active vasoconstriction in the leg that contributes to the exercise pressor response.

A 5 minutes resting baseline will be obtained prior to the subject performing IHE at 30% MVC sustained to fatigue. An oscilloscope will be calibrated to provide the subject visual feedback on force generation; subjects will be verbally encouraged to maintain force throughout; fatigue will be determined by the investigators as maximal perceived rating of exertion accompanied by inability to maintain target force for more than 3 sec, despite continued effort.

In those with SCI, given the lack of vascular sympathetic control and thus no increase in sympathetic outflow during tilt, cold pressure, and isometric handgrip exercise, we expect that bone blood flow will respond as a pressure passive system and hence will track blood pressure response.

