*Sympathetic Microneurography.* Multiunit, post-ganglionic muscle sympathetic nerve activity will be recorded with a tungsten microelectrode in the peroneal nerve only in the able-bodied population. The peroneal nerve will be mapped at the fibular head via low voltage transcutaneous electrical stimuli. Subsequently, the microelectrode is inserted manually through the unanesthetized skin and initially provides low voltage electrical stimuli (1-4 volts) to help locate the nerve. When the microelectrode enters a nerve fascicle innervating muscle, involuntary twitches are induced. The microelectrode is then used to record sympathetic efferent nerve outflow to calf muscle. This procedure is safe and the principal investigator has performed over 1000 experiments since 1991 without complication. The raw nerve signal will be amplified, rectified and integrated for visual inspection during experiments (Nerve Traffic Analyzer, Model 662c-3, University of Iowa Bioengineering, Iowa City, IA) and the amplified raw signal will be directly sampled at 20 kHz for further signal processing.

*Beat-by-Beat Calf Blood Flow.* We will use Doppler derived flow velocities to estimate whole limb blood flow through the popliteal artery. A continuous wave 4 MHZ Doppler probe (Multidop T2, DWL) is placed against the skin under the knee to isolate the popliteal artery proximal to the bifurcation.

*Electrocardiogram.* A standard 4-lead electrocardiogram will be used to obtain continuous heart rate.

*Arterial Pressure.* The arterial waveform in a finger of the hand will be derived on a beat-to-beat basis by the Finapres Blood Pressure System (Finapres, Ohmeda) with brachial oscillometric blood pressure (Dash 2000, GE) as a standard measure of arterial pressure.

*Respiration.* A respiratory belt will be placed around the chest for breathing depth and frequency. This signal does not provide exact tidal volumes and will only be used to monitor breathing.

Following the removal of instruments, the able-bodied volunteers will be asked to complete the online MSNA questionnaire administered via REDCap, if the patient had the electrode placed

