#### Statistics

Data from NIRS monitoring will be used to determine hemoglobin content changes in tibial bone from changes in light absorption on a moment-by-moment basis. A detailed description of the analysis can be found in our previous work. [12] Briefly, NIRS monitoring provides a change in hemoglobin content from one state to another. This is due to the fact that absolute intensity of the scattered light measured across the tibia cannot be used for an absolute measure of perfusion. However, as perfusion increases, there is a proportional increase in absorption (and vice versa). Thus, percent change in total hemoglobin detected reflects the relative change in perfusion.

The main outcomes assessed will be tibial perfusion, whole leg blood flow, and sympathetic activity. Descriptive statistics of the time series of these outcomes will include mean, median, standard deviation, and range. Differences/relations will be considered statistically significant at alpha = 0.05 level.

For cold pressor test, isometric handgrip exercise, and head tilt, in able-bodied we will assess the relationship between dependent increases in sympathetic outflow and changes in tibial perfusion. Since it is unclear whether absolute or relative changes in sympathetic outflow may best relate to relative changes in tibial flow, both will be explored as within subject predictors. Sex-related differences in response will be assessed simply as group differences in the individual slopes of the relation between tibial flow and sympathetic activity.

For cold pressor test, isometric handgrip exercise, and head tilt, in those with SCI we will assess the relationship between changes in mean arterial pressure and changes in tibial perfusion.

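### Second protocol: the SCI entry criteria set no lower limit on injury level, yet the analysis assumes that no SCI participant keeps sympathetic outflow to the leg

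*Combined protocol and SAP*

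**What the plan says.** All references are to the second protocol in the combined document.

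- **III. Subject Selection, Inclusion criteria.** SCI participants are men aged 18 to 40 "with injuries American Spinal Injury Association Impairment Scale (AIS) A and B and C, with full hand function". No neurological level is given.
- **Exclusion criteria.** The conditions added for SCI are that "those with SCI will have no extreme spasticity to avoid spontaneous contractions and cannot be on baclofen due to its potential autonomic effects". Neither refers to level.
- **I. Background and Significance.** SCI serves as a human model of "chronic reduced loading with loss of sympathetic regulation below the level of injury".
- **V. Study Procedures, Detailed procedures.** "All those with SCI enrolled in this study will have complete injuries and thus vascular sympathetic control is disrupted below the level of injury". For that reason, "in those with SCI we will not record muscle/bone sympathetic activity". The microneurography paragraph under Measurements agrees: activity is "recorded with a tungsten microelectrode in the peroneal nerve only in the able-bodied population".
- **V, section on increased outflow with increased systemic pressure.** The group is expected to follow pressure passively, "given the lack of vascular sympathetic control and thus no increase in sympathetic outflow during tilt, cold pressure, and isometric handgrip exercise".
- **VI. Statistical Analysis, Statistics.** For the three stimuli, "in those with SCI we will assess the relationship between changes in mean arterial pressure and changes in tibial perfusion". There is no term, subgroup or sensitivity analysis for injury level.

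**The concern.** The SCI group serves as the condition in which leg vessels receive no sympathetic drive. By the protocol's own wording the loss lies below the injury, so whether it reaches the leg depends on where the injury is. The criteria do not fix that. Full hand function, which the handgrip test needs, limits how high the injury can be and so tilts the sample toward lower injuries. Nothing limits how low it can be.

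Followed exactly, the plan can therefore place men who do not meet its premise in the pressure-passive analysis and in the aim 3 comparison with able-bodied participants. A weak perfusion-on-pressure relation in the SCI group, or a small contrast with the able-bodied group, would then be hard to interpret. It could reflect bone physiology or the mix of injury levels enrolled.

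**Working it through.** **Step 1: the texts side by side.**

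| Question | What the second protocol provides |
|---|---|
| Who enters? | AIS A, B or C with full hand function; no level (Inclusion and Exclusion criteria) |
| Where is control lost? | Below the injury (Background; Detailed procedures) |
| What is assumed at the leg? | No rise in outflow in any SCI participant (section on increased systemic pressure) |
| Is it checked? | No nerve recording in SCI; no autonomic test listed |
| Does the analysis allow for it? | Arterial pressure against tibial perfusion only (Statistics) |

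The second row makes loss at the leg depend on level, the first leaves level open, and the third assumes the loss for everyone. The last two rows contain nothing that would reveal the gap.

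**Step 2: can such a man enter?** Assume that leg sympathetic outflow leaves the cord at lower thoracic and upper lumbar segments. A man with a complete injury below those segments, full hand function, no baclofen and no extreme spasticity meets every SCI-specific criterion and could keep central control of his leg vessels. Completeness does not exclude him. An incomplete injury (AIS B or C) above those segments is a second, separate route to preserved outflow.

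**Step 3: the plan's own figure.** The Sample Size section gives 17 men with SCI. That number is carried over from a calculation on able-bodied exercise data. The pilot size, effect and standard deviation are not reported, so it cannot be reproduced. It is used here only as the denominator.

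**Step 4: dilution of the mean slope.** Let b be the mean perfusion-on-pressure slope in men without leg outflow, k the number of the 17 who keep it, f = k/17, and c·b the mean slope in those k men.

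- Group mean slope = (1 − f)·b + f·c·b = b·[1 − f(1 − c)].
- Proportional fall = f(1 − c).
- The documents give neither k nor c. Both are assumed: k = 2, 3 or 5 and c = 0.5, 0 or −1.

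| k | f = k/17 | c = 0.5: f/2 | c = 0: f | c = −1: 2f |
|---|---|---|---|---|
| 2 | 0.118 | 6% | 12% | 24% |
| 3 | 0.176 | 9% | 18% | 35% |
| 5 | 0.294 | 15% | 29% | 59% |

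If c = 1 the fall is zero.

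**Step 5: the aim 3 contrast.** If the k men respond on average exactly as able-bodied participants do, the mean difference between groups shrinks by f, that is 12%, 18% or 29%. No power figure is attached. The Statistics section names no test for this comparison, and the 17 was not derived for it.

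**The case against.** The strongest reply is that Detailed procedures already says every SCI participant has a complete injury. That does not answer the point. The sentence is not an entry criterion, it does not fit AIS B and C, and a complete injury below the leg outflow would still spare it.

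Other objections stand and limit the point:

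- **Identification.** A reader might infer that affected men could never be identified because nerve activity is not recorded. The documents do not support that. Neurological level can be established in the examination that gives the AIS grade, so men could be separated by level afterwards. Popliteal flow is also measured in SCI and gives an indirect view of the leg vascular response. What is missing is a requirement to record level and a planned use for it.
- **Physiology.** A reader might take it as fact that these men would vasoconstrict in bone as pressure rises. That is the protocol's hypothesis, and its Background says that no human studies have been done. With outflow and pressure rising together, their net slope could still be positive, which is why c = 0.5 is in the table.
- **Reversal.** A reader might infer that the pressure-passive hypothesis would be rejected because of enrolment. The figures show dilution: even the most adverse case leaves 1 − 0.59 = 41% of the slope, with its sign unchanged. The Statistics section gives no rejection rule, and the passive response is worded as an expectation.
- **Anatomy and counts.** The spinal segments and the values of k are assumptions, not figures from the documents.

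**Conclusion.** The point holds as a gap between entry criteria and analysis premise. No level criterion and no level-based analysis supports the assumption that leg sympathetic outflow cannot rise in any SCI participant. The protocol's own description makes that assumption depend on level.

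The consequence, conditional on the protocol's hypothesis, is dilution of the SCI perfusion-on-pressure relation and of the aim 3 contrast. Its size is unknown. The illustrated range for the mean slope is a fall of 6% (2 of 17, slope half as large) to 59% (5 of 17, slope equal and opposite). This rests on the assumed segmental anatomy, the assumed counts and the assumed slopes. The conflict between AIS A, B and C and the statement that all injuries are complete is part of the same problem, because settling level alone would not secure the premise. The change should be made before the SCI data are analysed.

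**What to change.** 1. In Study Procedures, require neurological level to be recorded with the AIS grade for every SCI participant.
2. In Statistics, define the pressure-passive analysis and the aim 3 comparison on SCI participants whose injury lies above the leg sympathetic outflow, at a level the investigators fix in advance. Report the others separately. Alternatively, make this an entry criterion in Subject Selection.
3. Reconcile the Inclusion criteria (AIS A, B and C) with Detailed procedures (all complete), so that entry and premise agree on completeness as well as level.

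The text change is a few lines. The cost is fewer participants in the main SCI analysis, or a smaller recruitment pool. The documents give no distribution of injury levels, so that number cannot be estimated. With 17 planned, the investigators should check it against their own referral records before choosing between the two options.
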